8.3 Analysis Populations

The primary efficacy population will be the Full Analysis Set (FAS) that will include all randomized and treated subjects. Following the intent-to-treat philosophy, subjects will be analyzed within the treatment group to which they are randomized.

The primary safety population will be all treated subjects. For safety analyses, subjects will be classified based upon the treatment received.

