The Itch NRS is an instrument for measurement of itch intensity that asks subjects to rate the intensity of their itch on an 11-point scale ranging from 0 (no itch) to 10 (worst itch imaginable) during a 24-hour recall period. Both WI-NRS and AI-NRS during a 24-hour recall period will be captured. The daily NRS results will be summarized at Weeks 2, 4, 6 and follow-up as outlined in [Section 2.4](#). A 4-point responder is a subject who had at least a 4-point reduction in score between the visit and baseline. A 3-point responder is similarly defined.

2.3.3 *Static Patient Global Assessment of Itch Severity*

The sPGA assesses overall itch severity by asking the severity of itchiness in the past 7 days on a 5-point scale as none (0), mild (1), moderate (2), severe (3), and very severe (4).

2.3.4 *Patient Global Impression of Change in Itch Severity*

The PGIC in Itch Severity is a single item measure that assesses the change in overall itch severity since the Baseline visit on a 7-point scale from (very much better) to (very much worse).

2.3.5 *ItchyQoL*

ItchyQoL is a 22-item pruritus-specific instrument that measures the degree to which pruritus affects quality-of-life. The responses to the items are Never (1), Rarely (2), Sometimes (3), Often (4) and All the Time (5). This impact is quantified into 3 subscales (symptom, function, emotion) and an overall score. A higher score corresponds to a more adverse impact. The overall score is the average of the 22 items. If an item is missing the total score will be missing. The score for each subscale is the average score for the items that make up the subscale. The items that make up the subscales are,

- Symptom subscale score (items 1-6):
 - My itchy skin condition bleeds,
 - My skin hurts because of my itchy skin condition,
 - My itchy skin condition burns or stings,
 - I get scars from my itchy skin condition,

- I need to scratch my itchy skin condition,
- Temperature/seasonal changes aggravate my itchy skin condition
- Function subscale score (items 7-13):
 - I spend a lot of money treating my itchy skin condition,
 - My itchy skin condition makes it hard to work or do what I enjoy,
 - My itchy skin condition affects my interaction with others,
 - My itchy skin condition affects how well I sleep,
 - My itchy skin often makes it difficult to concentrate,
 - My itchy skin condition limits the types of clothes I can wear,
 - My itchy skin condition forces me to buy special soaps, detergents, and lotions.

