Visit	Range (complete data)	Extended Range
Baseline	Day -7 to -1	Day -11 to -8
Week 2	Day 8 to Day 14	Day 15 to Day 18
Week 4	Day 22 to Day 28	Day 29 to Day 32
Week 6	Day 36 to Day 42	Day 43 to Day 46

An additional ‘Follow-Up’ timepoint will also be created. This timepoint includes the last 7 post treatment observations that are at least 7 days after the end of treatment.

For the WI-NRS and AI-NRS endpoints results from within the windows provided in [Table 4](#) and at Follow-up may not be used based upon the confounding logic outlined in [Section 2.6](#).

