2.5.1 Primary Analysis

The difference in the primary efficacy outcome measure (WI-NRS change from baseline to Week 6) between treatment groups will be tested using an analysis of variance (ANOVA) model controlling for the stratification factors. A main effects model with an interaction term (treatment by stratification factors) and a Type II hypothesis will be used. More precisely this ANOVA model uses the following as a stratified adjusted measure of the change from baseline for a given treatment group:

$$\Delta = \sum_{j=1}^4 \frac{n_{1j}n_{2j}}{n_{1j}+n_{2j}} \Delta_j ,$$

where j represents the stratification cells, n is the sample size for treatment 1 and 2 and Δ_j is the change measure for stratum j . Should a site make an error during randomization and select the wrong stratification factor (e.g. select the White stratification cell for a non-White subject) the test will use how the subject was randomized. All other summaries of race (e.g. baseline characteristics or subgroup analyses) will be based upon the correct race group and not the as randomized group.

Conceptually the hypotheses being tested for this study are:

$$H_0: \Delta_{Placebo} \geq \Delta_{Serlopitant} \quad H_a: \Delta_{Placebo} < \Delta_{Serlopitant}$$

where $\Delta_{Placebo}$ is the placebo change from baseline to Week 6 and $\Delta_{Serlopitant}$ is the similar measure for serlopitant. Each serlopitant treatment group (1 mg and 5 mg) will be compared to placebo separately.

The primary endpoint will utilize the analysis windows outlined in [Section 2.4](#), the confounding rules outlined in [Section 2.6](#) and the missing data rules outlined in [Section 2.7](#).

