2.5.2 Secondary Analyses

The differences between treatment groups for the key secondary endpoints will be tested using the same ANOVA model as used for the primary endpoint (change in ItchyQoL) or a Cochran Mantel Haenszel (CMH) test (WI-NRS 4-point responder rate) controlling for the 'as randomized' stratification factors. A CMH test will also be conducted for the WI-NRS 3-point responder rate, AI-NRS 4-point responder rate, and AI-NRS 3-point responder rate.

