2.6 Confounding Event

The use of excluded therapies / procedures or clinically significant changes in the dose or frequency of allowed adjunctive therapies can result in a change in pruritus. In the statistical plan the use of excluded therapies / procedures or clinically significant changes in the dose or frequency of allowed adjunctive therapies is called a confounding event. Short treatment (up to 3 days) of an excluded medication for indications other than atopic dermatitis or pruritus (see protocol for specific medications) is not considered a confounding event. Should a confounding event occur, the cause of changes in pruritus can no longer be clearly attributed to the randomized treatment. As such, the results from the WI-NRS/AI-NRS following this confounding event (i.e. on the day the confounding event occurred or after) will not be included in the analysis.

Confounding events will be identified by a blinded clinical review of the concomitant medication and procedures data prior to database lock.

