2.7 Handling of Missing Data

Summary statistics will generally be reported based upon observed data. Should a determination of treatment period (on treatment, pre-treatment) be required for adverse events or concomitant medication but the corresponding date is missing, or is a partial date,

the event/medication will be considered on treatment unless the portions of the data that are available indicate this is not possible.

If a subject fails to complete their eDiary for a week or more, or a confounding event occurs the WI-NRS and AI-NRS endpoints, including the primary endpoint, may be missing. In this case, their change from baseline value will be imputed. The subject's data prior to confounding will be used. From that point forward their trajectory will be imputed based upon the trajectory of their treatment group. The imputation approach first determines the average change for each time point (i.e. Weeks 2, 4, 6) for each treatment group. The difference between weeks n-1 and n will be considered the change for Week n. These change measure will be used to 'fill in' the missing weeks between the last completed week (pre-confounding) and Week 6. Hence, a placebo subject who receives excluded therapy in Week 4 will have their Week 6 WI-NRS change from baseline imputed as $\Delta_4 + \Delta_{(4,6)}$, where Δ_4 is the observed change from baseline result for the subject up to Week 4 and $\Delta_{(4-6)}$ is the placebo change from Week 4 to 6 (i.e. the average placebo decrease from Week 4 to 6).

Missing data imputation will only be used for the WI-NRS and AI-NRS endpoints.

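### The formal Week 6 ItchyQoL test is a complete-case ANOVA with no missing-data method or sensitivity analysis, so it leaves out treated subjects whose earlier scores are collected

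*SAP*

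**What the plan says.** - **Status of the endpoint.** SAP 1.6 places ItchyQoL third at each dose, after the primary endpoint and the WI-NRS 4-point responder rate. SAP 2.5.2 has it "tested using the same ANOVA model as used for the primary endpoint (change in ItchyQoL"), and SAP 3.4.3 repeats this for Week 6.
- **Missing values.** SAP 2.7: "Missing data imputation will only be used for the WI-NRS and AI-NRS endpoints". For the ItchyQoL overall score, SAP 2.3.5 adds: "If an item is missing the total score will be missing".
- **Sensitivity analyses.** SAP 2.8 plans multiple imputation, exclusion without imputation, LOCF and BOCF, all for WI-NRS. None is planned for ItchyQoL.
- **Population.** Protocol 8.3: "The primary efficacy population will be the Full Analysis Set (FAS) that will include all randomized and treated subjects". SAP 3.1 bases the efficacy analyses on the FAS unless otherwise specified.
- **Collection.** Protocol Appendix A, Table 3 schedules ItchyQoL at screening, baseline, Weeks 2, 4 and 6, the early treatment discontinuation (ETD) visit and follow-up. SAP Table 3 accepts Days 36 to 57 as Week 6.
- **Confounding events.** SAP 2.6 removes "the results from the WI-NRS/AI-NRS following this confounding event". It does not mention ItchyQoL.

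**The concern.** The primary endpoint has a rule that gives subjects without Week 6 diary data a value. ItchyQoL goes through the same ANOVA without one, so a subject with no usable Week 6 total contributes nothing, even if baseline, Week 2 and Week 4 questionnaires are complete. The analysis is nominally on the FAS but in effect on a subset selected after randomization.

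Two things are at stake. Precision is lost that the earlier scores could partly restore. And if subjects without a Week 6 score responded differently from the rest, to an extent that differs by arm, the estimated difference is biased. No planned sensitivity analysis would show this for ItchyQoL.

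**Working it through.** **1. The plan's own figure.** SAP 1.6 gives 150 per group, effect 1, SD 2.9, one-sided 5% and 90% power for the primary test. The standard error is 2.9 × √(2/150) = 0.335, and 1/0.335 = 2.986. Power is Φ(2.986 − 1.645) = 0.910, or 0.909 with the noncentral t. The figure reproduces. The documents give no effect, SD, missing rate or power for ItchyQoL, so steps 3 and 4 rest on assumptions.

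**2. Who lacks a Week 6 score.** Protocol 6.5.9 sets follow-up 28 ± 3 days after the ETD visit, or on Days 40–46 for subjects stopping before Day 15. Set against the Day 36–57 window, and assuming no separate Day 43 diary prompt after an ETD visit:

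| Situation | Follow-up | Week 6 ItchyQoL |
|---|---|---|
| Drug stopped before Day 15 | Day 40–46 | Yes, if attended |
| ETD Day 15–26 | Day 40 to 57 | Yes, if attended |
| ETD Day 27–32 | Day 52 to 63 | Depends on the visit date |
| ETD Day 33–35 | Day 58 or later | None (the ETD score falls in Week 4) |
| ETD Day 36 or later | – | The ETD score counts |

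SAP Table 1 could be read as giving everyone a Day 43 entry, which would close the gap at Days 27–35. Withdrawals from the study, missed entries and incomplete questionnaires stay uncovered on either reading.

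**3. Precision.** With a share m missing in both arms, the standard error grows by 1/√(1 − m). At m = 15% this is 1/√0.85 = 1.085. For power, assume a standardized ItchyQoL effect equal to that of the primary, 1/2.9 = 0.345 SD:

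| Missing | Per arm | Power (one-sided 5%) |
|---|---|---|
| 0% | 150 | 90.9% |
| 5% | 142 | 89.5% |
| 10% | 135 | 88.1% |
| 15% | 128 | 86.6% |
| 20% | 120 | 84.6% |
| 25% | 112 | 82.3% |

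These are upper limits on what a better method could restore, because Weeks 2 and 4 only partly predict Week 6.

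**4. Bias.** Suppose that missing subjects improve by g SD less than observed ones, in both arms. Each arm's observed mean then overstates improvement by (share missing) × g, so the complete-case difference is shifted in favour of serlopitant by

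b = (m_serlopitant − m_placebo) × g.

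| Missing: placebo / serlopitant (assumed) | g (assumed) | b (SD) |
|---|---|---|
| 10% / 10% | any | 0 |
| 10% / 15% | 0.5 | 0.05 × 0.5 = +0.025 |
| 10% / 20% | 0.5 | 0.10 × 0.5 = +0.05 |
| 15% / 5% | 0.5 | −0.10 × 0.5 = −0.05 |

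Against an assumed effect of 0.345 SD, these shifts are 0.025/0.345 = 7% and 0.05/0.345 = 14%. The sign follows the imbalance in missingness, which the documents do not give.

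**The case against.** **The plan made an explicit choice.** SAP 2.7 says that summaries generally use observed data and reserves imputation for the two itch scales. That is a stated rule, not an oversight. This stands, but the rule leaves a formally tested endpoint with neither a method that uses the earlier scores nor a sensitivity analysis.

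**Stopping treatment mostly does not mean a missing score.** Step 2 bears this out, and it limits the size of the problem. It does not cover withdrawals, missed entries, voided totals or some late discontinuations.

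**Type I error.** A reader might infer that the false-positive rate rises well above 5%. Taken alone, the 10%/15% scenario with g = 0.5 has a standard error of √(1/135 + 1/127.5) = 0.1235 SD and a shift of 0.025/0.1235 = 0.20, so P(Z > 1.645 − 0.20) = 7.5%. The documents do not support this as the error rate of the trial. ItchyQoL counts only after the primary and the responder rate succeed at that dose. If WI-NRS has no true effect and its test is unbiased, the chance that both the primary and ItchyQoL reject is 1.0%, 1.6% or 2.5% at assumed test correlations of 0.3, 0.5 or 0.7, before the responder step lowers it further. The stand-alone rate matters only if the drug moves WI-NRS and responders but not ItchyQoL. With the imbalance reversed (15%/5%, g = 0.5), even the stand-alone rate is 2.0%, below nominal.

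**Direction.** The only discontinuation counts by arm are those for adverse events in TCP-101 (Protocol 1.3.2): 3 of 64 on placebo, 1 of 65 on 1 mg and 2 of 64 on 5 mg. They are too few to settle the direction, and they do not suggest greater loss on active drug.

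**Confounding events.** A reader might also infer that ItchyQoL wrongly keeps scores after excluded therapy. The SAP never says so; it is read from silence in 2.4 and 2.6. Keeping such scores would be a legitimate treatment-policy approach, consistent with the intent-to-treat philosophy in Protocol 8.3. Endpoints in a gatekeeping sequence need not share an estimand. What stands is that the choice is not stated.

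**Conclusion.** The point holds in limited form. As written, the Week 6 ItchyQoL test is complete-case and has no sensitivity analysis for missing scores, so it does not use all of the FAS.

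The loss of precision follows from any missingness: about 8% on the standard error at an assumed 15% missing, with power falling from 90.9% to 86.6% if the standardized effect equals that of the primary. Bias is possible but of unknown size and sign. It vanishes when missing shares and response gaps are equal across arms, and it is 0.025 to 0.05 SD in the scenarios shown. All missing rates and response gaps are assumptions.

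The documents do not support a claim that the trial's error rate is inflated, or that retaining scores after a confounding event is an error. The primary conclusion is untouched. This is a worthwhile, inexpensive improvement to the last-ranked formal test, not a flaw that undermines the trial.

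**What to change.** Amend SAP 2.5.2, 2.7 and 3.4.3 before unblinding:

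1. Base the Week 6 ItchyQoL test on multiple imputation, or on a repeated-measures model, using baseline, Week 2 and Week 4 ItchyQoL, treatment and randomization stratum. All FAS subjects with a baseline score then contribute. With multiple imputation, the planned ANOVA can be kept within each completed data set and the treatment differences combined.
2. Keep the observed-case ANOVA as a sensitivity analysis.
3. State whether ItchyQoL scores after a confounding event are kept or excluded, and report the alternative as sensitivity. This is a choice of estimand, and items 1 and 2 apply either way.

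The cost is SAP wording and some programming; multiple imputation is already planned for WI-NRS in SAP 3.4.2. The downside is reliance on a missing-at-random model: bias is removed only so far as the earlier scores, treatment and stratum explain why Week 6 is missing.

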2.8 Sensitivity Analyses, Subgroups and Covariates

Descriptive statistics for the change in WI-NRS at Week 6 will be provided for the subgroups indicated below. Forest plots of the difference and confidence interval for this difference will also be created. The subgroups include,

- Sex
- Age Group (< 18 years, 18 to 64 years, > 64 years)
- Race
 - All race groups with less than 30 subjects will be combined with 'Other'
 - A White versus Non-White comparison will be made
- Baseline WI-NRS
- Baseline IGA-AD
- Use of allowed concomitant medications as outlined in Section 5.7.1 of the protocol
- Treatment completion (completed treatment, did not complete treatment).

To investigate the impact of missing data / confounding sensitivity analyses will be performed for the WI-NRS endpoint. These methods include,

1. Multiple imputation, MI, methods will be used to recalculate the p-values at Week 6.
2. The summary statistics will be produced where the missing data is imputed using
 - a. Data after the confounding event are excluded with no imputation

- b. Last Observation Carried Forward (LOCF),
- c. Baseline Observation Carried Forward (BOCF).

2.9 Safety Analyses

Safety endpoints will be summarized with descriptive statistics. All safety summaries and analyses will be performed using the safety population.

Prior and Concomitant medications will be coded by the World Health Organization (WHO) Drug Dictionary version 2012/Q4. Adverse Events and Medical History will be coded using MedDRA version 17.1 (or later).

2.10 Interim Analysis

An independent Data Monitoring Committee (iDMC) will monitor unblinded safety data. The iDMC may make recommendations to the Sponsor to continue or terminate the study based upon the outcomes of the data reviews. The iDMC is not tasked with stopping the study early for efficacy or for stopping for futility. Greater detail concerning the iDMC can be found in the iDMC charter.

3 SUMMARY TABLES, LISTINGS, AND FIGURES

3.1 General Conventions

Unless otherwise stated, summary statistics including the number of subjects (n), mean, standard deviation, median, minimum and maximum will be presented for continuous variables. Generally, the minimum and maximum values will be presented to the same decimal precision as the raw values, the mean and median values to one more, and the standard deviation, to two more decimal places than the raw values. For categorical variables, per category, the absolute counts (n) and percentages (%) of subjects with data. Percentages will be presented to one decimal place.

For AEs, medical history (prior and concomitant diseases) and concomitant medications reported on a per-subject basis, the denominator for the percentage calculation will be the number of subjects at risk in each treatment group. A subject will be considered at risk if the subject is in the analysis set and in the subgroup of interest.

All p-values will be rounded to 4 decimal places. If a p-value is less than 0.0001 it will be displayed as “< 0.0001”, a p-value rounding to 1 will be displayed as “> 0.9999”.

Unless otherwise specified all summaries will be performed by treatment group, all efficacy analyses will be based upon the FAS population and all safety will be based upon the safety population. The safety and demographic tables will include a total serlopitant (1 mg and 5 mg doses) and a total column (total serlopitant and placebo) along with the treatment columns.

3.2 Definition of Baseline

Unless specified elsewhere, baseline is defined as the last available measurement prior to administration of study drug. For events that occur on the same day as the first administration of study drug (i.e. assessments performed at the Baseline visit) the assessment will be classified as pre-treatment and hence baseline. Baseline for the daily measures recorded in the eDiary and actigraphy device is defined in [Table 4](#).

3.3 Clinical Study Subjects

3.3.1 Subject Disposition and Analysis Populations.

The number of subjects randomized, treated, and discontinued early, will be summarized within all randomized subjects. The reason for early termination will be summarized. Additionally, a summary of subjects present at each visit as determined by the presence of a vital signs result, will be provided.

A listing of entry criteria that were not met will be produced. The listed criteria will include the criteria language. A table of the violated entry criteria for randomized subjects will be produced as well as a table that summarizes the screen failure reasons for screen failure subjects.

The number of subjects in each analysis population will be summarized.

3.3.2 *Demographics and Baseline Characteristics*

Demographic and baseline characteristics will be summarized descriptively by treatment group. This will include the following items:

1. Demographic variables

- a. Age
- b. Race
- c. Ethnicity
- d. Sex
- e. Height
- f. Weight
 - Baseline WI-NRS
 - Presence or absence of active AD
 - Baseline IGA-AD
 - Age at AD diagnoses
 - AD severity relative to prior 3 and 12 months
 - Family history of atopy (eczema, asthma, allergic rhinitis)
 - Prior Treatments of AD (e.g. antibiotics, antihistamines, corticosteroids, biologics, immunomodulatory agents)

3.3.3 *Concomitant Medications and Procedures*

Medications and procedures with a stop date before the treatment dosing date will be considered prior medications/procedures. Medications/procedures with a start or stop date on or after the treatment dosing date will be considered concomitant. All medications/procedures marked as ongoing are concomitant.

A medication/procedure with an incomplete stop date will be considered concomitant if:

1. Month is missing and year is equal to or after the year of treatment dosing date
2. Day is missing and year is equal to the year of the treatment dosing date and month is equal to or after the month of the treatment dosing date.

All concomitant medications will be summarized by treatment group. All medications, including prior medications, will be provided in listings.

A table and listing will be produced to summarize confounding events as defined in [Section 2.6](#).

A table and listing will be produced to summarize the allowed concomitant medications (antihistamines, topical steroids, topical calcineurin inhibitors, emollients).

A table and listing will be produced to summarize topical adjunctive therapies.

Procedures and non-medication therapies will be listed. A listing of confounding procedures / non-medication therapies will be provided.

3.3.4 Medical History

Medical history will be tabulated by system organ class, preferred terms and treatment group.

3.3.5 Clinical Study Treatment

The total tablets used, duration of treatment (Last dose date – first dose date + 1), number of subjects with dosing errors and compliance (see [Section 2.2](#)) will be summarized. Tablets used will be calculated by summing the number of days the subject indicates medication was used and based upon tablet counts reported in the CRF. For the first treatment day of the diary-based calculation, if a subject indicates they used treatment it will be assumed three tablets were taken. The kit numbers provided in the eDC system will be used to identify dosing errors. Should an error occur the tablet counts provided in the eDC system will be used to determine treatment assignment for the safety population.

